**BLOOD ALERGY SAMPLES**  
 Table 14.3.3.6 Blood allergy samples Cohort A Analysis Set: SAF  
 Table 14.3.3.6 Blood allergy samples Cohort B Analysis Set: SAF  
**PHYSICAL EXAMINATIONS**  
 Table 14.3.4.1.1 Physical Examinations, Cohort A Analysis Set: SAF  
 Table 14.3.4.1.2 Physical Examinations, Cohort B Analysis Set: SAF  
**ELECTROCARDIOGRAMS**  
 Table 14.3.5.1 12-Lead Electrocardiography/ Lead II Rhythm Strip, Cohort A Analysis Set: SAF  
 Table 14.3.5.2 12-Lead Electrocardiography/ Lead II Rhythm Strip, Cohort B Analysis Set: SAF

## 20.2 Listings

Below is Table of Contents for the Listings.

Listing 16.2.1 Patient Completion/Discontinuation Analysis Set: SAF  
 Listing 16.2.2 Minor and Major Protocol Deviations Analysis Set: SAF

QMS Document Name: Statistical Analysis Plan	Page 27 of 29
QMS No (include version ref): STF-015-GL.02	Document date: 09JUL2019
CONFIDENTIAL	

Listing 16.2.3 Subject Allocation to Trial Populations And Eligibility Assessment Analysis Set: FAS  
 Listing 16.2.4 Demographic Data and Baseline Characteristics Analysis Set: SAF  
 Listing 16.2.5 Medical History and Concomitant Diseases Analysis Set: SAF  
 Listing 16.2.6.1 Previous and Concomitant Medication (Part 1) Analysis Set: SAF  
 Listing 16.2.6.2 Previous and Concomitant Medication (Part 2) Analysis Set: SAF  
 Listing 16.2.7 Exposure and compliance Analysis Set: SAF  
 Listing 16.2.8 Clinical benefit for intraoperative nerve visualization Analysis Set: FAS  
 Listing 16.2.9 Dose Limiting Toxicity Analysis Set: FAS  
 Listing 16.2.10.1 All Adverse Events (Part 1 ) Analysis Set: SAF  
 Listing 16.2.10.2 All Adverse Events (Part 2 ) Analysis Set: SAF  
 Listing 16.2.10.2 Serious Adverse Events Analysis Set: SAF  
 Listing 16.2.10.3 Adverse Events Leading to Withdrawal of Study Medication Analysis Set: SAF  
 Listing 16.2.10.4 Adverse Events Leading to Discontinuation from Trial Analysis Set: SAF  
 Listing 16.2.10.5 Adverse Events Leading to Death Analysis Set: SAF  
 Listing 16.2.11 Vital Signs, Oxygen Saturation and Body Temperature Values Analysis Set: SAF  
 Listing 16.2.11 Vital Signs, Oxygen Saturation and Body Temperature – Values Outside of Reference Ranges Analysis Set: SAF  
 Listing 16.2.12 Laboratory Values Analysis Set: SAF  
 Listing 16.2.12 Laboratory Values Outside of Reference Ranges Analysis Set: SAF  
 Listing 16.2.12.3 Urinalysis Values Analysis Set: SAF  
 Listing 16.2.13 Childbearing Potential and Pregnancy Test Results Analysis Set: FAS  
 Listing 16.2.14 Electrocardiography 12-Lead ECG/Lead II Rhythm Strip Analysis Set: SAF  
 Listing 16.2.14 Electrocardiography 12-Lead ECG/Lead II Rhythm Strip – Clinically Significant Findings Analysis Set: SAF  
 Listing 16.2.15 Chest X-Rays/CT Analysis Set: SAF  
 Listing 16.2.16 Physical Examination Analysis Set: SAF  
 Listing 16.2.17.1 Surgical Imaging Worksheet (Part 1) Analysis Set: FAS  
 Listing 16.2.17.2 Surgical Imaging Worksheet (Part 2) Analysis Set: FAS  
 Listing 16.2.18 SBR Analysis Set: FAS

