### **5 Analysis Sets and Cohorts**

Analysis Sets are described as follows:

- Enrolled analysis set (ENR) defined as all subjects who provided informed consent.
- Safety Analysis Set (SAF), defined as all subjects who received at least one dose of ALM-488

QMS Document Name: Statistical Analysis Plan	Page 9 of 29
QMS No (include version ref): STF-015-GL.02	Document date: 09JUL2019
CONFIDENTIAL	

- Dose-Limiting Toxicity (DLT) Evaluable Set, defined as subjects who receive ALM-488 and either 1) complete the safety follow-up through the DLT evaluation period (i.e., Day 15 ± 8) or 2) experiences a DLT at any time during the DLT evaluation period.
- Activity Analysis or Full Analysis Set (FAS), defined as all subjects in SAF who also received at least one evaluable image.
- Pharmacokinetics (PK) Analysis Set defined as all subjects who completed a PK blood sampling period without any major protocol violations which would render the data unreliable. The PK will be the primary analysis set for the pharmacokinetic analyses. PK of analyses will be fully described in the PK SAP.

SAF will be used for all safety analyses. FAS will be used for all efficacy analyses. The PK Analysis Set will be used for all PK analyses; ENR set will be the primary analysis set for disposition and listings. PP set will constitute the primary analysis set for early efficacy. DLT Evaluable Analysis Set will be used to assess the tolerability of ALM-488 in the dose escalation phase.

The Dose Escalation/De-Escalation cohort (Cohort A) consists of all dose escalation/de-escalation cohorts: Cohort A1, A2, A3, A4, A5, A6. In case of DLT rate = 0 or special FDA requests additional cohorts may be added to the tables.

The Dose Time Determination cohort (Cohort B) consists of: Cohort B1 - dose administration 3-5 hours in advance of surgery, and Cohort B2 - dose administration 1-3 hours in advance of surgery.

If not otherwise stated in the respective section, the statistical analyses will be performed for the following analysis sets:

Analyses	ENR	FAS	DLT	SAF	PK
Disposition	✓				
Demographics and baseline characteristics				✓	
Medical history				✓	
Exposure and compliance				✓	
Previous and concomitant therapies				✓	
Early Efficacy		✓			
Pharmacokinetic					✓
Safety				✓	
Dose-Limiting Toxicity			✓		
Listings		✓		✓	

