## 9 Patient Accounting and Disposition

### 9.1 *Patient accounting*

The number and relative frequencies of subjects in each Cohort will be presented overall, by Analysis Sets, and individual Cohorts (i.e., Cohorts: A, A1, A2, A3, A4, A5, A6, B, B1, and B2 ), including individual reasons of exclusion from the respective analysis set.

A list of subjects' first ALM-488 infusion date time start, date time end, time to discontinuation and reasons for discontinuation will be presented.

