#### SUBJECT DISPOSITION

- Table 14.1.1 Reasons for Screen Failure, cohort A Analysis set: ENR
- Table 14.1.2 Summary of Analysis Sets and Cohorts Analysis Set: ENR
- Table 14.1.3 Disposition and Discontinuation Reasons [1], Cohort A Analysis Set: ENR
- Table 14.1.3 Disposition and Discontinuation Reasons, Cohort B Analysis Set: ENR
- Table 14.1.4 Disposition by Site, Cohort A Analysis Set: ENR
- Table 14.1.4 Disposition by Site, Cohort B Analysis Set: ENR

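### The DLT listing is on the FAS, so a treated subject with a DLT but no evaluable image is left out of it

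*SAP*

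**What the plan says.** SAP Section 20.2 assigns the DLT listing to the activity set: "Listing 16.2.9 Dose Limiting Toxicity Analysis Set: FAS". Section 12 promises a listing of DLTs directly after the dot plot of Cohorts A1 to A6, without naming an analysis set.

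Section 5 defines the two sets concerned. The FAS is "defined as all subjects in SAF who also received at least one evaluable image". The DLT Evaluable Set takes a subject who received ALM-488 and either completed follow-up through the DLT period (Day 15 ± 8) or "experiences a DLT at any time during the DLT evaluation period". No image is required, and the definition names no cohort.

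On use, Section 5 says that the "DLT Evaluable Analysis Set will be used to assess the tolerability of ALM-488 in the dose escalation phase", and that safety analyses are done on the SAF. Its table ticks the DLT set for dose-limiting toxicity, and ticks FAS and SAF in a general row for listings. The adverse event listings are on the SAF, for example "Listing 16.2.10.1 All Adverse Events (Part 1 ) Analysis Set: SAF". Figure 14.3.1, the DLT dot plot, is on the DLT set.

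**The concern.** A toxicity listing should not depend on whether imaging succeeded. The link between the two need not be accidental. Cohort B is dosed 1-3 or 3-5 hours before surgery, so a serious acute reaction can cancel the operation and with it every image. The plan treats both elements as possible: it tabulates infusion reactions (Section 14.1) and counts subjects completing surgery separately (Section 9.2). The FAS filter could therefore remove a DLT because of its own consequences.

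Safety is the primary objective, and a zero DLT count is one of the two conditions for the Optimal Dose in Section 12. A reader will expect a listing titled Dose Limiting Toxicity to be complete.

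**Working it through.** **1. Who is dropped.** Take a subject who received ALM-488, had a DLT in the evaluation period and has no evaluable image.

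| Set | Condition in Section 5 | Included? |
|---|---|---|
| SAF | received ALM-488 | yes |
| DLT Evaluable | treated, and DLT in the period | yes |
| FAS | SAF plus at least one evaluable image | no |

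The FAS gains nothing in return. Any treated subject with a DLT in the period is already in the DLT Evaluable Set, so for a listing of DLT events the FAS can only remove subjects.

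**2. Where that subject still appears.** The DLT items named in Sections 20.1 to 20.3 are no tables, one listing (16.2.9, FAS) and one figure (14.3.1, DLT set).

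| Output | Cohort A | Cohort B |
|---|---|---|
| Listing 16.2.9 (FAS) | omitted | omitted |
| Figure 14.3.1 (DLT set) | solid red dot | not covered (Section 12: A1 to A6) |
| SAF adverse event tables and listings | event shown | event shown |
| Named DLT output left | the figure | none |

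The Cohort B column matters only if DLTs are assessed in Cohort B.

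**3. Cohort sizes.** From Section 4.1: Cohort B is 2 × 6 = 12. Cohort A is 3 × 3 = 9 to 6 × 6 = 36. The total is 9 + 12 = 21 to 36 + 12 = 48. All agree with the plan. Cohort B is 12/48 = 25% to 12/21 = 57% of the trial.

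**4. How often.** This cannot be derived from the documents. As an illustration only, let p be the DLT rate and q the chance that a subject with a DLT has no evaluable image. Both are assumed. If DLTs are assessed in Cohort B and subjects are independent, the chance that the listing omits at least one of the 12 is 1 − (1 − pq)^12:

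- p = 0.05, q = 0.05: 1 − 0.9975^12 = 3.0%
- p = 0.10, q = 0.20: 1 − 0.98^12 = 21.5%
- p = 0.20, q = 0.50: 1 − 0.90^12 = 71.8%

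The spread shows that the answer is set by the assumptions. With the listing on the DLT Evaluable Set or the SAF, no subject is omitted for want of an image, whatever p and q are.

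**The case against.** The best defence is that little is hidden. The event stays in the SAF adverse event outputs, and an infusion reaction in Cohort B would also be counted in the Cohort B version of Table 14.3.1.3. An affected Cohort A subject keeps the red dot. Section 9.1 adds set sizes by cohort: "The number and relative frequencies of subjects in each Cohort will be presented overall, by Analysis Sets, and individual Cohorts", with reasons for exclusion, and Section 20.1 has "Table 14.1.2 Summary of Analysis Sets and Cohorts Analysis Set: ENR". An FAS one smaller than the DLT set, with a reason attached, would point to the gap. All of this stands, and it limits the point to the DLT label of an event. The cross-check is incomplete at subject level, because the allocation listing is also on the FAS: "Listing 16.2.3 Subject Allocation to Trial Populations And Eligibility Assessment Analysis Set: FAS".

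The FAS label also agrees with the general listings row in Section 5. That row allows SAF as well, and the specific row for dose-limiting toxicity names the DLT set, so it does not justify the choice. The pregnancy test listing (16.2.13) is oddly on the FAS too, which suggests a clerical slip. Section 20.2 is only a contents list. The separate output specification mentioned in Section 2.1 was not supplied and may already carry a DLT flag or a corrected label.

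For Cohort B, Section 5 ties the use of the DLT set to dose escalation, and Section 12 places the listing beside the escalation dot plot. DLTs may simply not be assessed there. Against that, neither the set definition nor the listing title is limited to Cohort A. The text is ambiguous, so the Cohort B part has to stay conditional.

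**Conclusion.** Wrong as written, severity minor. The analysis set of Listing 16.2.9 conflicts with the dose-limiting toxicity row of Section 5 and with its general rule for safety analyses, and it can leave a DLT out of the listing meant to show DLTs. That conclusion rests only on the set definitions. The loss is of the identification as a DLT, not of the event, and in Cohort A the figure makes it good. If DLTs are assessed in Cohort B, no other DLT output named in Section 20 would do so for B1 and B2.

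A reader might infer that the trial would report a false zero DLT rate in the 12 Cohort B subjects. The documents do not support this: no planned output gives a Cohort B DLT rate or interval, and such a figure would arise only if a reader divided the FAS listing by the DLT-set count. Nor does any section plan a DLT rate or interval pooled over Cohorts A and B, so there is no such analysis to criticise. The absence of a DLT table is not a defect either. Cohort A has none, and a dot plot with a complete listing is adequate for cohorts of 3 to 6.

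**What to change.** In Section 20.2, put Listing 16.2.9 on the DLT Evaluable Set, or on the SAF. In Section 5 or 12, state whether DLTs are assessed in Cohort B. If they are, say that the listing covers all cohorts, and optionally add B1 and B2 to Figure 14.3.1. Carry the same label into the separate output specification. The dose selection rule stays as it is.

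The cost is one label and at most one sentence. No new data are needed for the relabel. Covering Cohort B assumes that DLT status is recorded there or can be derived from its adverse event data, which the supplied text does not confirm.

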### 20.3 Figures

Below is Table of Contents for the Figures.

Figure 14.3.1 Dot Plot of Dose Limiting Toxicities by Dose Analysis Set: DLT  
 Figure 14.3.2 Scatter Plot of Intensity Ratios by Time of Injection to Skin Incision and by Dose Analysis Set: FAS  
 Figure 14.3.3 Scatter Plot of Intensity Ratios by Nerve Diameter and by Dose Analysis Set: FAS  
 Figure 14.3.4 SBR for WLR and FL Analysis Set: FAS

### 22 Appendices

QMS Document Name: Statistical Analysis Plan	Page 28 of 29
QMS No (include version ref): STF-015-GL.02	Document date: 09JUL2019
CONFIDENTIAL	

**Appendix I: Normal ranges for vital signs, oxygen saturation and body temperature**

Parameter	LLN	ULN
Blood pressure (diastolic)	50 mmHg	90 mmHg
Blood pressure (systolic)	90 mmHg	140 mmHg
Pulse rate	60 bpm	100 bpm
Respiratory rate	10 bpm	20 bpm
Oxygen saturation	92 %	100 %
Body temperature	35.0 °C	38.0 °C

LLN = lower limit of normal, ULN = upper limit of normal, bpm = beats per minute.

LLNs and ULNs for pulse rate, respiratory rate, oxygen saturation and body temperature are taken from [2].

QMS Document Name: Statistical Analysis Plan	Page 29 of 29
QMS No (include version ref): STF-015-GL.02	Document date: 09JUL2019
CONFIDENTIAL
